Study Phases	(1) Screening : Participants in the Mood, Mother, and Infant study are invited to participate in the Mood, Mother, and Child follow-up study. Those who meet inclusion criteria are scheduled for a mother-only visit for the Inhaled Oxytocin and HPA Axis Reactivity sub study.
Screening	
Study Treatment	(2) Intervention : Non-pregnant women will be randomized to either 24 IU of nasal OT or placebo prior to the Trier Social Stress Test.
Follow-Up	(3) Follow-up : Effects of nasal OT will be measured during the study visit, which will last about 2 hours.
Efficacy Evaluations	This is not a treatment study; this is a translational study to test the effect of oxytocin on the HPA axis.
Pharmacokinetic Evaluations	NA
Safety Evaluations	Prior to and during a 90-minute period following intranasal OT or placebo, mothers will be monitored for vital signs (heart rate, blood pressure, ear temperature), vascular resistance and mood.
Statistical And Analytic Plan	We will use a general linear model to test the hypothesis that participants who are randomized to receive nasal oxytocin experience lower HPA reactivity, operationalized using CRT area under the curve (AUC) during the TSST, to evaluate this proposed causal pathway
Data And Safety Monitoring Plan	Study PI, [name], will provide medical oversight for the randomized trial of oxytocin vs. placebo. Any adverse events, as well as any significant deterioration in mood, health or wellbeing, will be reported directly to [name] (the PI). All moderate and severe adverse events will be reported within one week to the FDA, whether anticipated or unanticipated.

3. Background and Rationale

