3.4. Relevant Literature and Data

Perinatal depressive symptoms are associated with dysregulation of the HPA axis. Jolley et al¹¹ measured ACTH and cortisol during an exercise stressor at 6 and 12 weeks postpartum and found expected correlations between ACTH and cortisol among euthymic women (N=13), but not among women with depressive symptoms (N=9). Heinrichs compared lactating mothers who breastfed vs. held their infants 30 minutes before the TSST and found that recent breastfeeding blunted cortisol, but not ACTH¹². This blunting is thought to be mediated by oxytocin, and a growing literature implicates dysregulation of OT in PND. Findings in our laboratory using extracted samples demonstrate an inverse association between OT during breastfeeding and maternal

symptoms of depression and anxiety at 2 months postpartum¹³. We further found that OT AUC differentially impacted HPA axis activity during the TSST in women with or without mood symptoms¹⁴. These results implicate OT and HPA axis dysregulation in the psychobiology of perinatal depression; in the proposed study, we will determine whether these differences persist at 6 to 8 years postpartum.

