5.2. Intervention/Treatment procedure for study visit

Non-pregnant women will be randomized to either 24 IU of nasal oxytocin (OT) or placebo. The Investigational Drug Service (IDS) will use a random number generator to prepare a randomization table. Participants will be block randomized by risk status at enrollment in the Mood, Mother and Infant (MMI) study, as verified by structured clinical diagnostic interview (No history of depression or anxiety, Past depression or anxiety, current depression or anxiety). Both participants and study personnel will be blinded to allocation group. At the end of the protocol, participants will be asked which condition they believed they were in ('oxytocin,' 'control,' 'not sure') to ascertain success of blinding. Forty minutes after treatment, women will undergo the Trier Social Stress Test (TSST), comprised of a speech task and a math task; the TSST reliably induces large and consistent HPA and cardiovascular responses^{16,17}. The TSST is administered as follows: Pre-Task Instructions: (5 minutes) Subjects will be introduced to 3 people (the 'selection committee') and asked to assume the role of a job applicant. Anticipation Period: The subject prepares her speech for 3 minutes in the presence of the committee. Speech: The committee asks the subject to deliver her talk for 5 minutes while being video and audio-recorded. If the subject finishes early, the committee

responds with prepared questions to ensure that she speaks for the entire 5 minutes. These questions are designed to be non-harassing but to create a feeling of lack of predictability/controllability (e.g., "Do you have any enemies?") Serial Subtraction (PASST): The committee will ask the subject to subtract the number 7 from 2000 as quickly and accurately as possible for 5 minutes. For each mistake, the committee says "Stop -- mistake -- start over at 2000." Stress Recovery: The subject sits quietly alone for 20 minutes.

- 5.3. Follow- up procedures : NA**
- 5.4. Unscheduled visits: NA**
- 5.5. Concomitant Medication documentation: NA**
- 5.6. Rescue medication administration (if applicable): NA**
- 5.7. Subject Completion/ Withdrawal procedures**

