5.14. Statistical Methods

Our primary objective is to test the extent to which nasal oxytocin compared with placebo alters the trajectory of CRT during the TSST. We will use repeated measures analysis to quantify the effects of group (OT vs. placebo) on CRT trajectory during the TSST. We will first establish the shape of unconditional trajectory models for CRT using generalized linear mixed models with a random intercept and slopes to account for individual differences in CRT trajectories. We will test the fit of quadratic, cubic, and exponential effects of time as well as linear spline models. The most parsimonious unconditional trajectory model that fits the data well will be used for hypothesis testing. The intercept of the CRT trajectories will be placed at peak CRT. We will regress growth parameters (intercept and slopes) on treatment arm. A significant effect of treatment arm on the intercept will indicate a difference in peak CRT across groups, and a

significant effect of treatment arm on slopes will indicate differences in the rate of recovery during the TSST.

For secondary endpoints, we will similarly use repeated measures analysis to quantify the effects of group (OT vs. placebo), time, and group x time on each measure's trajectory during the TSST. We will use repeated measures analysis with an interaction term to test the extent to which maternal depression/anxiety and OXTR genotype modifies the effect of oxytocin vs. placebo on measures of stress reactivity.

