5.15. Sample Size and Power

Our projected sample size is 150 participants whose cortisol is assessed 8 times during the visit. Heinrichs et al (2001) assessed the effect of breastfeeding vs. holding a baby on cortisol levels among postpartum women undergoing the Trier Social Stress Test. Cortisol levels were similar prior to the social stressor, and then diverged, with values that were 1.03, 1.22, and 0.73 standard deviations higher among those who had held their baby compared with those who had breastfed. Because CRT growth parameters are individual-level parameters, power for detecting the effect of individual randomization to treatment arm on CRT trajectories can be simplified into an independent samples t-test. We used SAS 9.4 to estimate the minimum detectable difference for a two-sample t-test based on sample size, with 80% power and an alpha of 0.05. With only 30 participants per group, we are powered to detect a standardized effect of 0.74 standard deviations (Table). This effect is in line with the smallest plausible effect size in Heinrichs et al.

Table: Minimum detectable difference by N per group

N per Group	30	35	40	45	50	55	60	65	70	75
Mean Diff	0.74	0.68	0.63	0.60	0.57	0.54	0.52	0.50	0.48	0.46

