5.16. Interim Analysis: NA

6. Study Intervention (Device, Drug, or Other Intervention)

The study drug and placebo are obtained from Apotheke Roter Ochsen (Schaffhausen, Switzerland). The study drug was shipped to the UNC Investigational Drug Service, which took responsibility for storage, distribution, drug return and destruction.

7. Study Intervention Administration (If Applicable)

Randomization: Non-pregnant women will be randomized to either 24 IU of nasal oxytocin (OT) or placebo. The Investigational Drug Service (IDS) will use a random number generator to prepare a randomization table. Participants will be block randomized by risk status at enrollment in the Mood, Mother and Infant (MMI) study, as verified by structured clinical diagnostic interview (No history of depression or anxiety, Past depression or anxiety, current depression or anxiety).

Masking: Participants will receive a nasal insufflation bottle of oxytocin intranasal spray or placebo intranasal spray manufactured to mimic oxytocin nasal spray. A licensed provider will supervise administration of the study drug. Both participants and study personnel will be blinded to allocation group. At the end of the protocol, participants will

be asked which condition they believed they were in ('oxytocin,' 'control,' 'not sure') to ascertain success of blinding.

8. Safety Management

Study PI, [name], will provide medical oversight for the randomized trial of oxytocin vs. placebo. In addition, a licensed provider will administer the study drug and be present for the Mother Visit. If a participant reports an unanticipated problem or adverse event, [name] will be notified immediately, and she will follow-up directly with the participant. If medical intervention is required, treatment allocation will be disclosed to the participant. The study coordinator will monitor AEs at study visits, tabulating events weekly. Any adverse events, as well as any significant deterioration in mood, health or wellbeing, will be reported directly to [name] (the PI). All moderate and severe adverse events will be reported within one week to the FDA, whether anticipated or unanticipated.

9. Data Collection and Management

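### Randomisation is blocked by three-level risk status, but no planned model carries a term for it; if risk status predicts cortisol, the arm-only standard errors are too wide and some precision is lost

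*Combined protocol and SAP*

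**What the plan says.** On randomisation, section 5.2 states "Participants will be block randomized by risk status at enrollment in the Mood, Mother and Infant (MMI) study", and section 7 repeats this. The three levels are "No history of depression or anxiety, Past depression or anxiety, current depression or anxiety". Section 4.2 describes the allocation without mentioning the blocking, but does not contradict it.

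On analysis, section 5.14 fits an unconditional trajectory model for cortisol and then states "We will regress growth parameters (intercept and slopes) on treatment arm". For the secondary endpoints it will "quantify the effects of group (OT vs. placebo), time, and group x time". The synopsis describes a different model for cortisol area under the curve ("We will use a general linear model to test the hypothesis that participants who are randomized to receive nasal oxytocin experience lower HPA reactivity"), also without a risk-status term. Section 5.15 says that power "can be simplified into an independent samples t-test", again unadjusted.

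Mood status enters a model in one place only, the sentence in section 5.14 that begins "We will use repeated measures analysis with an interaction term to test the extent to which maternal depression/anxiety and OXTR genotype". That sentence concerns effect modification, which section 5.13.3 classes as exploratory. It does not say whether the variable is the status used for randomisation or a later measurement.

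**The concern.** The analysis should reflect the way participants were allocated. When randomisation is blocked within strata, the arms are nearly balanced on the stratum factor, so differences between strata contribute almost nothing to the true sampling variance of the arm contrast. A model with treatment arm alone does not know this: it counts the between-stratum variation as residual noise and reports a standard error that is too large. Confidence intervals are then wider than they need be, and the nominal 5% test rejects less than 5% of the time under the null.

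At stake is precision, not validity. There is a smaller, second point: the plan neither includes nor rules out covariates, so whether to adjust for the blocking factor is not expressly settled before the data are seen.

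**Working it through.** **Inputs.** From section 5.15: 150 participants, taken as 75 per arm (the ratio is not stated, but the table ends at 75 per group); alpha 0.05, taken as two-sided because that reproduces the table; power 80%; one growth-parameter value per participant, compared by t-test. Assumed, because the documents give no value: R², the share of growth-parameter variance explained by risk status, over 0 to 0.20.

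**Reproducing the plan's own figures.** A two-sided two-sample t-test (noncentral t) at 80% power gives a detectable difference of 0.736 SD at 30 per group (stated 0.74), 0.566 at 50 (stated 0.57) and 0.4605 at 75 (stated 0.46). Power at the stated differences lies between 79.5% and 80.8% in all ten columns. The table is sound as an unadjusted calculation.

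**Formulas, with total SD 1 and n = 75 per arm.**

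- Standard error reported by the arm-only model: √(2/75) = 0.1633, whatever the R².
- True standard error under blocking: 0.1633 × √(1 − R²). At R² = 0.10 this is 0.1633 × 0.9487 = 0.1549.
- Excess width of the reported standard error: 1/√(1 − R²) − 1. At R² = 0.10 this is 5.4%.
- True size of the arm-only 5% test: 2 × [1 − Φ(1.96/√(1 − R²))]. At R² = 0.10 this is 2 × [1 − Φ(2.066)] = 3.9%.
- Power at 0.46 SD: noncentrality 0.46/[0.1633 × √(1 − R²)]. The adjusted model uses the critical value 1.976 (146 df). The arm-only model (148 df) in effect uses 1.976/√(1 − R²). At R² = 0.10 the noncentrality is 2.969, and the critical values are 1.976 (adjusted) and 2.083 (arm-only).

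| Assumed R² | SE too wide by | True size | Power, arm-only | Power, adjusted | Points forgone | Detectable difference, arm-only / adjusted |
|---|---|---|---|---|---|---|
| 0 | 0% | 5.0% | 79.9% | 79.9% | 0.0 | 0.460 / 0.461 |
| 0.02 | 1.0% | 4.8% | 80.2% | 80.7% | 0.5 | 0.459 / 0.456 |
| 0.05 | 2.6% | 4.4% | 80.5% | 81.9% | 1.4 | 0.457 / 0.449 |
| 0.10 | 5.4% | 3.9% | 81.1% | 83.9% | 2.7 | 0.453 / 0.437 |
| 0.20 | 11.8% | 2.8% | 82.5% | 87.9% | 5.3 | 0.446 / 0.412 |

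Points forgone are taken from unrounded powers, so they can differ by 0.1 from the difference of the printed figures.

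**Check by simulation.** With 150 participants, permuted blocks of four within three strata (block size assumed), and stratum mixes of equal thirds or 50/30/20 (assumed), 10,000 trials per scenario gave arm-only against adjusted power at 0.46 SD of 80.5–80.7% against 81.8–82.2% (R² = 0.05), 81.0–81.6% against 83.9–84.3% (0.10) and 82.3–83.0% against 87.8–88.3% (0.20). Arm-only type I error was 4.2–4.3%, 4.0–4.1% and 2.8–3.0% respectively; the adjusted model stayed at 4.7–5.2%. In the null runs at R² = 0.20 the arm-only model reported a standard error of about 0.163 when the true value was 0.146–0.148.

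**At a larger effect.** At 0.73 SD, the smallest of the three differences cited in section 5.15, power at 75 per arm exceeds 99% under either model for every R² above.

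**The case against.** The strongest reply is that nothing is broken. An arm-only model is a legitimate pre-specified choice: its estimate is unbiased, its type I error is at or below 5%, and the planned 80% power at 0.46 SD holds at every R² to within rounding. This stands, and the point claims no more than lost precision.

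Second, the size depends wholly on an assumed R², and the documents give little ground for a large one. The mood evidence in section 3.4 concerns the correlation between ACTH and cortisol, and a relation between oxytocin and HPA activity that differs by mood symptoms. Neither is a reported shift in cortisol level or slope. The blocking factor is also a diagnostic category recorded some 6 to 8 years before this stress test, and the protocol treats persistence as open: "we will determine whether these differences persist at 6 to 8 years postpartum". This stands as a reason to expect the lower rows of R². It does not remove the case for adjusting, because the cost at R² = 0 is negligible.

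Third, the arithmetic treats each growth parameter as if observed without error. In the planned mixed model, estimation noise would dilute R²: with an assumed reliability of 0.7, a true R² of 0.10 acts like 0.07. This also stands, and makes the tabulated gains somewhat generous if R² refers to true between-person variance.

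Fourth, section 5.14 does name its regressors, so adding a covariate later would be a visible departure from the text. That weakens the worry about a choice made after the data are seen. It does not remove it, because the plan does not exclude covariates.

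**Conclusion.** The concern holds. The trial randomises within three risk strata, and no planned model for the primary or secondary endpoints has a term for them; the exploratory interaction does not fill the gap in the primary model. If risk status predicts a cortisol growth parameter, the arm-only analysis is conservative.

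The consequence is modest: roughly 1 to 5 points of power at 0.46 SD for R² between 0.05 and 0.20, nothing at R² = 0, and nothing of practical importance at 0.73 SD. These figures rest on an assumed R², on 75 per arm, on near-exact balance within strata, and on the plan's own reduction to a t-test on one value per participant. Neither validity nor the stated power is in question. The change is recommended because the gain, if there is one, comes almost free.

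**What to change.** Add to section 5.14 that the three-level risk status used for randomisation enters the primary cortisol model as a fixed effect on the intercept and slopes, and enters each secondary model as a fixed effect. State that its value is taken from the randomisation table, so that it cannot be confused with mood measured at the 6 to 8 year visit. Keep the arm-by-depression/anxiety interaction as a separate exploratory analysis, and date the change before unblinding.

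The cost is wording only. The variable already exists, and the adjustment uses two of about 148 degrees of freedom per growth parameter. If risk status turns out to be irrelevant, the loss is under 0.1 point of power. The power table can stay as it is.

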4.1. Study Design

This is Randomized Parallel Assignment Quadruple masked experiment to test the effect of inhaled oxytocin vs. placebo on HPA axis reactivity during a standardized social stressor, the Trier social stress test. Mothers who were enrolled in the Mood, Mother and Infant study will be eligible to participate in the 6-year follow-up maternal visit. At the time of this visit, mothers will be randomized to a single 24 IU dose of nasal oxytocin or placebo. Following administration of the study drug, women will participate in the Trier Social Stress Test (TSST), and blood samples will be collected to quantify HPA axis reactivity during a 90-minute period following study drug administration.

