All participants will also be reminded before starting the procedures that they would be free to withdraw at any time without penalty, and may contact our IRB review board or the Principal Investigator (numbers are provided) if she feels that rights regarding privacy or risk to health have been infringed. The right of the participants to withdraw from the study or to refuse any procedure will be made absolutely clear. The original consent form will be kept in a secured location in a locked office, and a copy will be provided to the participant.

- 5.8. Screen failure procedures**

Some mothers who are eligible for Inhaled Oxytocin and HPA Axis Reactivity are expected to be pregnant at the time of the follow-up study. Because oxytocin can cause contractions, the Inhaled Oxytocin and HPA Axis Reactivity visit will not be scheduled while the mother is known to be pregnant, and will be deferred until 6 months postpartum. All mothers without a known pregnancy will be screened with a urine pregnancy test on arrival to the Mother Visit; if the pregnancy test is positive, the nasal OT and TSST protocol will not be performed.

- 5.9. STUDY EVALUATIONS AND MEASUREMENTS**

Mobile Impedance Cardiographs (MindWare Tech Ltd, Gahanna, OH) will be used to measure cardiac rate, interbeat interval and pre-ejection period (PEP) in mothers and children. MindWare HRV software will be used to derive respiration and to calculate high frequency HRV and respiratory sinus arrhythmia from the IBI series as indices of parasympathetic activity. Respiratory rate will be used in all HRV analyses. MindWare Impedance Cardiography Analysis software will calculate cardiac time intervals (PEP, LVET), stroke volume and cardiac output. PEP will index sympathetic activation.

Blood will be collected at baseline, during the speech and math tasks, and at 10 and 20 minutes of recovery, as HPA-axis responses are reliably found 10-30 minutes following the TSST. Evidence regarding optimal timing of stress testing is conflicting. Visits will be scheduled for 1 pm to increase likelihood of detecting a stress response unopposed by the circadian influence, based on the experience of investigators in our laboratory and published studies of postpartum women. These investigators have found menstrual

cycle phase does not affect TSST results; therefore visits will not be scheduled based on cycle phase.

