At baseline, 40 minutes after nasal OT, at the end of the TSST, and at the end of recovery, participants will complete a brief task assessment questionnaire, rating on a scale of 0-10 to what extent they felt 1) Stressed, Worried, Nervous, or Tense; 2) Happy, Relaxed, Comfortable, or Satisfied; 3) Irritated, Annoyed, 'Pissed off,' or Furious; 4) Depressed, Sad, Down, or Unhappy; and 5) Overwhelmed, Unable to Control Things, or Discouraged.

At the end of the protocol, participants will be asked which condition they believed they were in ('oxytocin,' 'control,' 'not sure') to ascertain success of blinding.

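### The primary model in 5.14 makes no use of baseline cortisol to sharpen the peak contrast: a missed precision gain, available only if the baseline blood sample is drawn before dosing

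*Combined protocol and SAP*

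**What the plan says.** - Section 5.14 (Statistical Methods) fits a mixed model with a random intercept and random slopes to CRT. "The intercept of the CRT trajectories will be placed at peak CRT", and then "We will regress growth parameters (intercept and slopes) on treatment arm". The arm effect on the intercept is read as a difference in peak CRT, and the arm effect on the slopes as a difference in recovery. No covariate, change score or equal-baseline constraint is named.
- Section 5.9 on blood: "Blood will be collected at baseline, during the speech and math tasks, and at 10 and 20 minutes of recovery". It does not place the baseline draw before or after the spray.
- Section 5.9 on the mood questionnaire: "At baseline, 40 minutes after nasal OT, at the end of the TSST, and at the end of recovery". This separates baseline from the post-dose rating, but for the questionnaire only.
- Section 4.1 says that "blood samples will be collected to quantify HPA axis reactivity during a 90-minute period following study drug administration". Section 5.2 starts the stressor forty minutes after treatment, so a draw taken before the stressor could still be post-dose.
- Section 5.15 reduces power to an unadjusted two-sample t-test, with detectable differences from 0.74 SD at 30 per group to 0.46 SD at 75.
- The synopsis (section 2) describes a different analysis, a general linear model on CRT AUC. It also names no baseline covariate.

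**The concern.** A baseline value of the outcome is often the most useful covariate a randomized trial has. Here it is collected and then left unused for one of the two contrasts that 5.14 will interpret. It is natural to suppose that a mixed model already takes it in as the first repeated measure. For the peak contrast it does not, as shown in the working.

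What is at stake is precision. The smallest effect cited in 5.15 is 0.73 SD, from a study that "assessed the effect of breastfeeding vs. holding a baby on cortisol levels among postpartum women", not from nasal oxytocin. Section 3.3 reports that nasal-oxytocin studies gave varying results and included few women. If the true effect is smaller than 0.73 SD, or recruitment falls short of 150, the precision of the peak contrast begins to matter. Recruitment is limited to a cohort of 222, so extra power cannot easily come from extra participants.

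**Working it through.** **1. The plan's own figures.** Inputs from 5.15: alpha 0.05, 80% power, two-sample t-test. Two-sided testing and 1:1 allocation are assumed; two-sided reproduces the table. Power = 1 − F(t₀.₉₇₅; df = 2n−2, noncentrality d√(n/2)), solved for d at 80%:
- n = 30: 0.7356 (stated 0.74)
- n = 50: 0.5659 (stated 0.57)
- n = 75: 0.4605 (stated 0.46)

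All ten entries reproduce. At 0.73 SD, unadjusted power is 79% at 30 per arm, 95% at 50 and 99% at 75.

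**2. Why baseline as a response does not help under the planned model.** Take a linear spline (one of the shapes 5.14 allows) with its knot at peak, the same terms Z fixed and random, and arm free on all of them. With complete data, the variance of the arm contrast on the intercept is (2/n)[G₁₁ + σ²(Z′Z)⁻¹₁₁], where G₁₁ is the between-woman variance at peak and σ² the residual variance. The baseline-to-peak correlation ρ does not appear. At 75 per arm with G₁₁ = 1, the SE is 0.165-0.173 whatever ρ is, against √(2/75) = 0.163 for a plain t-test on the true peaks.

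**3. With the arms constrained equal at baseline.** Let t₀ be the baseline time measured from peak. The arm effect at baseline is β(intercept) + t₀β(rise). Setting it to zero gives β(rise) = −β(intercept)/t₀, which is one linear constraint.

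The draw times follow the 5.2 timeline: dose 0, stressor at 40, plus 5 min instructions, 3 min preparation, 5 min speech and 5 min arithmetic = 58, then recovery. This gives draws at 0, 53, 58, 68 and 78 min, assuming baseline at dosing and task draws at the end of each task.

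Other assumptions, none given in the documents:
- knot at 58 or 68 min
- baseline variance equal to peak variance
- recovery-slope variance 0.25 (time in 20-minute units), independent of the other terms
- residual variance 0.05, 0.10 or 0.25 of peak variance

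Detectable difference = SE ratio × 0.4605 (75 per arm) or × 0.7356 (30 per arm). The 0.30 SD effect is illustrative.

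| Assumed ρ | SE ratio, constrained/planned | Detectable SD, 75 per arm (planned 0.46) | Detectable SD, 30 per arm (planned 0.74) | Power at 0.30 SD, 75 per arm (planned 45%) |
|---|---|---|---|---|
| 0.1 | 0.996-0.998 | 0.46 | 0.73 | 45% |
| 0.3 | 0.958-0.973 | 0.44-0.45 | 0.70-0.72 | 47-48% |
| 0.5 | 0.877-0.917 | 0.40-0.42 | 0.65-0.67 | 51-55% |
| 0.7 | 0.740-0.822 | 0.34-0.38 | 0.54-0.60 | 60-69% |

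The t-test shortcut, with the SD multiplied by √(1−ρ²), gives 0.46, 0.44, 0.40 and 0.33 at 75 per arm. That is the upper limit of the gain. An assumed eight-draw schedule gives nearly the same SE ratios (0.958-0.975 at ρ = 0.3, 0.739-0.822 at 0.7). The recovery-slope SE is essentially unchanged (for example 0.1486 against 0.1485).

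**4. With estimated covariances.** REML fits were simulated with 500 null trials per cell, five draws, knot at 68 min and residual variance 0.10. At 75 per arm the empirical SE ratios were 1.01, 1.00, 0.96, 0.88 and 0.76 for ρ = 0, 0.1, 0.3, 0.5 and 0.7. Type I error was 0.044-0.056 planned and 0.044-0.054 constrained. At 30 per arm it was 0.038-0.062 and 0.040-0.060.

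**5. If the shape is wrong.** With an arm effect of zero until 40 min and a true peak difference of −0.46, the planned spline estimates −0.379, an attenuation of (0.46 − 0.379)/0.46 = 18%. The constrained model gives −0.380 to −0.393. The constraint adds no bias here, but neither model is immune to a poor shape.

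**The case against.** The best case against is that 5.14 is a coherent model, its peak contrast is protected by randomization, and at 0.73 SD the planned 150 already give 99% power. A larger stake has to be supposed: a smaller effect, or a recruitment shortfall that no passage forecasts. The size of the gain rests on a correlation the documents do not give, and at 0.1 there is none worth having. The remedy also depends on a pre-dose draw that the text does not confirm. The visit schematic in the Appendix, not shown in the text reviewed, may settle that.

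Most of this stands, and it limits the point to a recommended improvement. It does not remove it: where the draw is pre-dose the change costs almost nothing, and in the null simulations it did not inflate type I error.

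A reader might infer more than the documents support:
- That the primary analysis is biased or the power table wrong. Neither follows. The table reproduces, and the only bias seen comes from a misfitting trajectory shape, which the planned model has with or without the constraint.
- That the baseline blood is known to be pre-dose because the questionnaire's baseline is listed apart from the post-dose rating. That sentence is not about blood, and 4.1 describes blood sampling after dosing.
- That baseline could simply be a covariate on the growth parameters. With four post-dose draws as the response, this can do worse than the plan at correlations of 0.3 or less (0.44-0.47 SD at 0.3, 75 per arm, against 0.46).

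**Conclusion.** The point holds as a missed gain in precision for the peak contrast only. At 75 per arm the gain ranges from nothing (ρ = 0.1), through 0.01-0.02 SD (ρ = 0.3), to about 0.08-0.12 SD (ρ = 0.7) off a detectable difference of 0.46 SD. The documents do not say where in that range the trial lies. The figures assume 1:1 allocation, complete data, a linear spline and the variance components listed in the working. The gain matters mainly if the true effect is below 0.73 SD or recruitment falls toward 30 per arm. It is legitimate only if the baseline blood precedes dosing; adjusting for a post-dose value could remove part of the drug effect.

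**What to change.** Before unblinding:
1. State in 5.9, or by reference to the visit schematic, whether the baseline blood sample is drawn before the spray.
2. If it is pre-dose, prespecify in 5.14 that baseline CRT remains a response and that the arm means are constrained equal at baseline. The peak and recovery-slope contrasts are still tested and every time point is kept.
3. If it is post-dose, leave the model unchanged.
4. If the synopsis AUC analysis is the one that governs, the equivalent is to add pre-dose baseline CRT as a covariate in that general linear model. Its gain depends on the baseline-to-AUC correlation, also not given.

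The cost is a sentence or two of SAP wording and one coded constraint, with no new data. The price in estimation is that the arm effect on the rise slope is no longer estimated separately from the peak effect. The result still depends on the chosen trajectory shape. The number of draws (five named in 5.9, eight assessments counted in 5.15) is a separate matter and should be raised on its own.
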